#### **16.4. Subject Recruitment**

All types of subject recruitment or advertising information must be submitted to Xeris Pharmaceuticals or its designee and to the IRB for review and approval prior to implementation. Advertisements approved by the IRB may be used as recruitment procedures.

#### **16.5. Reporting of Safety Issues and Serious Breaches of the Protocol**

In the event of any prohibition or restriction imposed (i.e., clinical hold), or if the investigator is aware of any new information which might influence the evaluation of the benefits and risks of the investigational product, Xeris Pharmaceuticals should be notified immediately. In addition, the investigator will inform Xeris Pharmaceuticals immediately of any urgent safety measures taken by the investigator to protect study subjects against any immediate hazard, and of any serious breaches of this protocol.

## **17. DEFINITION OF END OF TRIAL**

LSLV is defined as the date the investigator reviews the last subject's final safety data and determined that no further evaluation is required for the subject to complete the trial.

## **18. PROCEDURES FOR MODIFYING THE PROTOCOL OR TERMINATING THE STUDY**

### **18.1. Protocol Modifications and Deviations**

The principal investigator and the sponsor's representative must sign this protocol and its amendments (if any) before initiating the study at a particular site. The investigator will make all reasonable efforts to comply with the written protocol. Protocol modifications to ongoing studies that affect the safety of subjects or that alter the scope of the investigation, the scientific quality of the study, the experimental design, dosing, study assessments, the number of subjects exposed to test drug, or subject selection criteria must be made only after consultation between Xeris Pharmaceuticals and the investigator. All protocol modifications must be reviewed and approved by the IRB before the revised protocol can be implemented. Emergency revisions that eliminate an apparent hazard to subjects do not require preapproval by the IRB. However, the IRB must be notified in writing as soon as possible after the modification has been made. A copy of this communication must be forwarded to Xeris Pharmaceuticals. All departures from the protocol must be fully documented in the source documents and the CRFs of the subjects involved.

### **18.2. Study Termination**

The study may be prematurely terminated at any time because of a regulatory authority decision, change in opinion of the IRB, safety problems, or at the discretion of Xeris Pharmaceuticals or the principal investigator. Circumstances that may warrant premature study termination include, but are not limited, to the following:

- Determination of unexpected, significant, or unacceptable risk to subjects,
- Failure to enter subjects at an acceptable rate,
- Insufficient adherence to the requirements of the protocol,
- Insufficient provision of complete and evaluable data, or
- Plans to modify, suspend, or discontinue development of the study drug.

If the study is prematurely terminated or discontinued, Xeris Pharmaceuticals will promptly notify the investigator documenting the reason for study termination, and specific procedures for termination will be arranged by the sponsor in coordination with the investigator. After notification, the investigator must contact all participating subjects within 7 days. All study materials must be collected and all CRFs completed to the greatest extent possible, and all study materials must be returned to Xeris Pharmaceuticals or its designee within an additional 28 days.

## **19. PUBLICATION OF STUDY RESULTS**

Publication of study results is discussed in the Clinical Study Agreement.

## APPENDIX 1. INJECTION SITE DISCOMFORT ASSESSMENT

[figure not shown]
### Faces Pain Scale – Revised (FPS-R)

*Investigative Site Instructions:* The subject should complete the FPS-R regarding injection site discomfort at both **10±5** minutes and **30±5** minutes following the injection of study drug, and again before the end of the clinic visit if the FPS score at **30±5** minutes is > 0. The subject completes the FPS by choosing the face that corresponds to their current level of pain. The goal is for the subject to report the amount of discomfort, if any, remaining at each time point, as opposed to reporting the transient pain associated with needle insertion.

Show the faces to the subject and provide the following instructions, using the words “hurt” or “pain,” whichever seems right for a particular subject:

**“These faces show how much something can hurt. This face [point to the face on far left] shows no pain. The faces show more and more pain [point to each from left to right] up to this one [point to face on far right] – It shows very much pain. Point to the face that shows how much you hurt right now.”**

Score the chosen face 0, 2, 4, 6, 8 or 10, counting left to right, so 0 = no pain and 10 = very much pain.

**Injection Site Discomfort Description and Duration Questionnaire**

*Study Personnel Instructions:* Question 1a should be completed by the subject at **10±5** minutes following the injection of study drug. Any subject reporting discomfort other than “none,” should complete question 1b. Any subject reporting duration of discomfort of “at least 10 minutes” should complete follow-up question 1c at the end of the study visit. The goal is for the subject to report the qualitative nature and duration of discomfort, if any, associated with injection of study drug, ignoring any transient pain associated with needle insertion.

*Subject Instructions:* Please answer question 1a and, if they apply to you, questions 1b and 1c. In answering these questions, you should ignore any pain from insertion of the needle.

1a. How would you describe any discomfort you felt from the study drug? (Check **all** that apply):

- None (**Please ignore question 1b.**)
- Pain (e.g., throbbing, soreness, muscle ache)
- Itching
- Tingling, twitching or numbness
- Irritation (e.g., burning, stinging)

Other or additional comments: \_\_\_\_\_

1b. About how long did the discomfort last after the injection? (Check one):

- Less than 1 minute
- 1-2 minutes
- 3-5 minutes
- 6-9 minutes
- at least 10 minutes (**Please complete question 1c before leaving the clinic.**)

1c. In total, how long did the discomfort last after the injection? (Please enter a number below):

\_\_\_\_\_ Minutes

## APPENDIX 2. DRAIZE SCALE

*Study Personnel Instructions:* The modified Draize Scale as shown in the table below will be used for physical examination/rating of abnormalities at the injection site.

The injection site should be examined for formation of both erythema and edema and results recorded in the Case Report Form. Evaluations of the injection site should be performed at 10±5 and 30±5 minutes post-treatment, and again at the end of the treatment visit (i.e., at approximately 180±5 minutes post-dosing) if any scores > 0 were noted at 30-minutes post-dosing.

Erythema Formation		Edema Formation	
Description	Score	Description	Score
No erythema	0	No edema	0
Very slight erythema Barely perceptible	1	Very slight edema Barely perceptible	1
Well defined erythema	2	Well defined edema	2
Moderate erythema	3	Moderate edema Raised approx. 1 mm	3
Severe erythema Beet redness to slight eschar formation	4	Severe edema Raised more than 1 mm and beyond exposure area	4

### **APPENDIX 3. INSTRUCTIONS FOR USE**

1 STUDY OVERVIEW

1.1 Study Objectives

This is a sequential efficacy and safety study of G-Pen™ (glucagon injection) in pediatric patients with Type 1 diabetes (T1D). In addition, the pharmacokinetics of G-Pen™ will be evaluated.

Subjects 2.0 to <18.0 years old with T1D receiving daily insulin for at least 6 months from the time of diagnosis will be enrolled to the multi-center study across three age groups (2.0-<6.0, 6.0-<12.0, and 12.0-<18.0 years). Subjects using insulin injections will be administered intravenous (IV) insulin and subjects using an insulin pump will have the basal rate increased to induce a low normal glycemic state (plasma glucose of <80 mg/dl). All subjects will then receive an age-appropriate dose of G-Pen™. Subjects aged 2.0-<12.0 will complete a single treatment visit and receive a 0.5 mg dose of G-Pen™. Subjects aged 12.0-<18.0 will receive a 1.0 mg dose of G-Pen™ at an initial treatment visit, and will also be given a 0.5 mg dose at a second treatment visit occurring 7-28 days later. The second visit comprises a secondary analysis. The study protocol consists of:

- Screening visit;
- Treatment 1 visit: One daytime clinical research center visit for subjects aged 2.0-<12.0 to receive a 0.5 mg dose of G-Pen™ and for subjects aged 12.0-<18.0 to receive a 1.0 mg dose;
- Treatment 2 visit (7-28 days after the first treatment): Only subjects aged 12.0-<18.0 will return for a second visit to receive a 0.5 mg dose of G-Pen™; and
- Follow-up phone call: The parent or guardian will be contacted by telephone within 3-14 days of completing each dosing visit or premature discontinuation.

Figure 1 further details the flow for study assessments. This document describes the analyses that will be performed to assess efficacy and safety of G-Pen™ for each age group.

1.1.1 Primary Objectives

The primary objective of this study is to assess the increase in plasma glucose of subjects from baseline to 30 minutes after G-Pen™ glucagon injection, without additional interventions. The assessment will be conducted in each of three age groups (2.0-<6.0, 6.0-<12.0, and 12.0-<18.0 years). The mean of the initial plasma glucose measurement <80 mg/dL and a second confirmatory measurement at least 5 minutes later after stopping the insulin infusion comprises the baseline measurement.

1.1.2 Secondary Objectives

The secondary objectives of this study are:

- Evaluate the pharmacodynamics (PD) of G-Pen™. Additionally, in the 12.0-<18.0 year-old age group, to independently assess the plasma glucose change from baseline to 30 minutes after administration of G-Pen™ at a dose of 0.5 mg.
- Determine the safety and tolerability of G-Pen™ for each age group.
- Evaluate the pharmacokinetics (PK) of G-Pen™. The PK analysis will be performed by another organization, IMD (See Appendix II).

1.2 Endpoints

1.2.1 Primary Endpoints

The primary endpoint for this study is an evaluation of the change in plasma glucose following treatment with G-Pen™ (glucagon injection), particularly to quantify the increase from baseline to 30 minutes post-dosing, in each of three age groups.

1.2.2 Secondary Endpoints

The secondary endpoints for this study are as follows:

- PK parameters, including: descriptive analysis of serum glucagon AUC_{0-180m} , C_{max} and T_{max} of the different age group and overall population. These analyses will be conducted by IMD (See Appendix II).
- PD characteristics, including: descriptive analysis of plasma glucose AUC_{0-90m} , C_{max} , T_{max} and time to achieve an increase in plasma glucose of at least 25 mg/dL for each age group. In addition, in the 12.0-<18.0 year-old age group, plasma glucose change from baseline to 30 minutes after administration of G-Pen™ at a dose of 0.5 mg will be evaluated.
- Safety-related endpoints including:
 - Vital signs, including blood pressure (BP) and heart rate.
 - Incidence of adverse events (AEs) and serious adverse events (SAEs).
 - Subjective injection site discomfort assessed using the Faces Pain Scale (FPS-R).
 - Subjects with sufficient comprehension will further describe the nature and duration of any injection site discomfort using a second questionnaire.
 - Erythema and/or edema formation at site of injection assessed by an investigator using the modified Draize Scale.

1.3 Sample Size

In the Phase 2 study XSGP-201, healthy normal adults were treated using the G-Pen™ after subject completed an overnight fast and presented with baseline plasma glucose values similar to the target levels (< 80 mg/dL) planned for this study. The mean increase in glucose at 30 minutes post-dosing was approximately 25 mg/dL (standard deviation = 18). Based on these assumptions, a sample size of 6 subjects per age group is required to provide 90% power to detect at least this change in the primary endpoint, i.e., an increase of plasma glucose from baseline to 30 minutes after treatment, assuming a type 1 error rate of 5%.

Therefore, approximately forty-eight subjects are anticipated to be screened for this study, and 36 (up to 12 per age group) will be enrolled and receive study treatment to achieve the goal of 18 evaluable subjects equally distributed (n=6 per age group) across the three age groups: 2.0-<6.0, 6.0-<12.0, and 12.0-<18.0 years old. Each age group is an independent clinical experiment with its own α -level of 0.05.

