
Data management and statistical analysis:
	
Data will be entered from the source (e.g Case Report Forms) into Advantage eClinical an Electronic Database Capture (EDC) system by site personnel. Data will be monitored remotely and at on-site visits by the Clinical Research Associate (CRA).
 
Both primary and secondary endpoints will be summarized descriptively within each of the 3 age groups. Mean, standard deviation, median, minimum and maximum will be presented for continuous variables. Count and percentage variables will be presented for discrete variables. The primary endpoint will also be compared to 0 change using a simple t-test.
 
Pharmacokinetic data will be analyzed descriptively by dose/age cohort.

Sample Size Determination:
	
Based on results of a prior study, G-Pen™ (glucagon injection) is expected to increase glucose by minimally 25 mg/dL from baseline within 30 minutes of administration in every subject. Assuming a standard deviation of 18 mg/dL, a

sample size of 6 subjects per cohort has been chosen to provide 90% power to detect an increase of plasma glucose from baseline to 30 minutes after treatment.

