## **13. DATA ANALYSIS AND STATISTICAL METHODS**

### **13.1. Sample Size Determination**

In Phase 2 study XSGP-201, healthy normal adults were dosed with G-Pen™ after an overnight fast with baseline plasma glucose values that were similar to the target (< 80 mg/dL) planned for this study. The mean increase in glucose at 30 minutes post-dosing was approximately 35 mg/dL (SD = 18). Based on these findings, a sample size of 6 subjects per cohort has been chosen to provide 90% power to detect an increase of plasma glucose from baseline to 30 minutes after treatment, assuming a type 1 error rate of 5%.

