#### **13.2.1. Primary endpoint**

The primary endpoint is the change in plasma glucose at 30 minutes post-dosing from baseline, which is defined as the average of the two plasma glucose measurements (i.e., -5 and 0 minutes) completed immediately prior to dosing. Last observation carried forward (LOCF) will be applied for subjects who drop out before 30 minutes post-dosing or who otherwise have missing primary endpoint data (e.g. missed blood draws). In addition to the descriptive summary, a simple t-test will be used to compare the glucose change from baseline to zero change within each of the 3 age groups.

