2.3 Efficacy Analysis

2.3.1 Efficacy Primary Endpoint

The primary endpoint is the change in plasma glucose at 30 minutes post-dosing from baseline, which is defined as the average of the two plasma glucose measurements (i.e., -5 and 0 minutes) completed immediately prior to dosing. In addition to the descriptive summary, a simple *t*-test will be used to test whether there is a significant change in glucose from baseline to 30 minutes within each of the three age groups (Table 7). All three tests are 2-sided with α -level of 0.05.

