3.2 Analysis Cohort

The efficacy and PD analyses will include all participants who completed the dosing visit with the following exceptions:

- Dosing visits during which a glucose-elevating intervention is given after administration of G-Pen™ will be included in the analysis, but the glucose values after the additional intervention post-dosing will be censored.
- For the efficacy analysis, if the additional intervention is given before 30 minutes post-dosing, then the 30-minute post-dosing measurement will be replaced with the last glucose measurement prior to the intervention.
- For the PD analysis., if the additional intervention is given shortly after administration of G-Pen™ (i.e., more than half of the glucose values is censored), the subject will be excluded from the analysis.

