3.6 Multiple Comparisons/Multiplicity

There is only one primary endpoint. Each age group is individually powered. No adjustments for multiple testing are planned.

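### SAP 1.3 claims 90% power with 6 per age group, but its own mean and SD give 77.5% under the planned 2-sided t-test; the SAP and protocol also disagree on the XSGP-201 mean (25 vs 35 mg/dL) and the number treated (36 vs 24)

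*SAP*

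**What the plan says.** The sample-size inputs and the planned test are in different sections, and the two documents differ.

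- **SAP 1.3**, on XSGP-201: "The mean increase in glucose at 30 minutes post-dosing was approximately 25 mg/dL (standard deviation = 18"). With a 5% type 1 error, it then says that "a sample size of 6 subjects per age group is required to provide 90% power to detect at least this change". It names neither the test nor its sidedness.
- **SAP 2.3.1** plans a t-test of the 30-minute change within each age group and adds: "All three tests are 2-sided", at an alpha of 0.05.
- **Protocol 13.1**, on the same study: "The mean increase in glucose at 30 minutes post-dosing was approximately 35 mg/dL (SD = 18"). It also chooses 6 per cohort for 90% power at 5%.
- **Protocol 13.2.1**: "a simple t-test will be used to compare the glucose change from baseline to zero change". Sidedness is not given.
- **Protocol synopsis**: on the basis of an unnamed prior study, the product "is expected to increase glucose by minimally 25 mg/dL from baseline within 30 minutes of administration in every subject", with SD 18, 6 per cohort and 90% power.
- **SAP 3.6**, where no multiplicity adjustment is planned: "Each age group is individually powered".
- **Number treated**, for the same 18 evaluable: about 24, up to 8 per cohort (protocol synopsis and 9.1), against 36, up to 12 per age group (SAP 1.3).

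**The concern.** With 6 subjects the t-test has only 5 degrees of freedom, so the choice between one and two sides, or between the t and the normal distribution, moves the power by many points. SAP 1.3 leaves that choice unstated, and the choice made in SAP 2.3.1 does not give the stated 90%.

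The key input is also in doubt. One study, one endpoint and one SD appear with two means that differ by 10 mg/dL, and the power conclusion turns on which is right. A reader cannot tell whether each age group is short of 90% or the SAP has simply recorded the wrong number.

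The difference in treated totals matters in its own right, because it is half as many children again (36/24 = 1.5). It also sets the largest number that could be analysed, since "The efficacy and PD analyses will include all participants who completed the dosing visit" (SAP 3.2).

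**Working it through.** **Inputs.** n = 6 per age group, mean 25 mg/dL, SD 18, alpha 0.05 (SAP 1.3); 2-sided t-test of the change against zero (SAP 2.3.1 and its Table 7 footnote); alternative mean 35 mg/dL, SD 18 (protocol 13.1).

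**Formula.** For a one-sample t-test, df = n − 1 and the noncentrality is (mean/SD) × √n. Two-sided power is the probability that a noncentral t variable with these parameters falls beyond ±t(0.975, df).

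**Step 1. Trying to reproduce 90% at mean 25, n = 6.** The noncentrality is (25/18) × √6 = 3.40, with df = 5.

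| Method | Result at n = 6 | Planned analysis? |
|---|---|---|
| 2-sided t, 0.05 | 77.5% | Yes |
| 1-sided t, 0.05 | 89.6% | No |
| 2-sided normal approximation | 92.5% | No |
| 1-sided normal approximation | 96.1% | No |

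The 2-sided normal formula for the required n gives ((1.960 + 1.2816) × 18/25)² = 5.45, which rounds up to 6. So the stated figure could have come from a one-sided t-test or from a normal-approximation n. Neither matches SAP 2.3.1. Simulation of 1,000,000 trials gave 77.6% for the 2-sided t-test and 89.6% for the one-sided t-test.

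**Step 2. Power of the planned 2-sided t-test, SD 18.**

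| n analysed per group | Mean 25 | Mean 35 |
|---|---|---|
| 5 | 64.8% | 89.4% |
| 6 | 77.5% | 96.3% |
| 7 | 86.2% | 98.8% |
| 8 | 91.8% | 99.6% |
| 12 | 99.2% | >99.9% |

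At mean 25, the smallest n that reaches 90% is 8. At mean 35 it is 6, so protocol 13.1 is consistent with its own inputs.

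**Step 3. What n = 6 does support.** Solving the 2-sided t power for 90% at SD 18 gives a detectable mean rise of 30.1 mg/dL at n = 6, 24.2 at n = 8 and 18.5 at n = 12. Equivalently, for a mean of 25 and n = 6 to give 90%, the SD would have to be 18 × 25/30.07 = 15.0.

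**Step 4. The synopsis.** It describes a minimum of 25 mg/dL for every subject. If that is read as the mean, the synopsis has the same shortfall as SAP 1.3. If it is read as a floor, the mean must be above 25, and the synopsis does not state what it is.

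**The case against.** The strongest reply is that SAP 1.3 never says 2-sided and speaks of an increase, so its 90% may come from a one-sided 5% t-test (89.6%). The fault would then be a mismatch with SAP 2.3.1, not bad arithmetic. That is a fair account of how the figure may have arisen. It does not rescue the figure, because the power statement would then describe a test that the SAP does not plan.

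Second, if 35 mg/dL is the true XSGP-201 mean, there is no shortfall. This stands: the documents do not show that the trial is underpowered, only that the SAP's statement does not follow from the SAP's inputs.

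Third, 77.5% applies to exactly 6 analysed per group, and more may be analysed. At either document's ceiling, power at 25 mg/dL exceeds 90%. This also stands, but SAP 1.3 attributes the 90% to 6, and the ceilings are not targets.

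Fourth, power has no bearing on type 1 error, so the decision not to adjust for multiplicity is not undermined; SAP 1.3 justifies it by treating each age group as an independent experiment. Agreed. What fails is the description in SAP 3.6 of each group as individually powered, if that means 90% on the SAP's inputs.

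Finally, the analysed set is slightly narrower than SAP 3.2 alone suggests. SAP 3.3 drops subjects with both baseline values missing, and protocol 7.3 counts a visit as completed only with a glucose value 30 or more minutes after injection. The wording of the fix should respect both.

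**Conclusion.** The concern holds. On the SAP's inputs and the SAP's test, power at the target of 6 per age group is 77.5%, which is 12.5 percentage points below the stated 90%. On the protocol 13.1 mean it is 96.3%. The difference between the documents is one of fact about XSGP-201 and cannot be settled from them. The treated total is likewise contradictory, 24 against 36.

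These figures assume normally distributed changes, a true SD of 18 and exactly the number analysed that is shown. The 77.5% is the power at the minimum target if the true mean rise is 25 mg/dL; it is not a forecast for the trial. Because the primary power claim is wrong as written under the planned test and its main input is contradicted, it needs correcting.

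**What to change.** 1. Check the 30-minute mean and SD in the XSGP-201 report, and use one pair of values in SAP 1.3, protocol 13.1 and the synopsis. In the synopsis, state the mean rather than a per-subject minimum.
2. Name the test in each sample-size section: one-sample t-test of the mean change against zero, 2-sided alpha 0.05.
3. Restate the power at 6 per group as about 78% if the mean is 25 mg/dL, or about 96% if it is 35. Alternatively, say that 6 subjects give 90% power for a mean rise of about 30 mg/dL.
4. Make the treated total agree between the documents, either 24 (up to 8 per cohort) or 36 (up to 12 per age group).
5. State that all subjects who complete the dosing visit are analysed, subject to the baseline exclusion in SAP 3.3. If 25 mg/dL is kept, add that power is 91.8% with 8 analysed per group and 99.2% with 12.

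**Cost.** One check of a study report and a few sentences of text. The planned test, endpoint and evaluable target do not change. If 25 mg/dL is kept, the stated power at n = 6 becomes less favourable. The SAP edits are simple. Edits to the protocol go through its section 18.1, which requires IRB approval of modifications and consultation between sponsor and investigator where the number exposed changes.
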